#### **4.4.6 Estimand for Annualized Relapse Rate**

**Estimand:** The estimand is the difference in the ratios of the annualized relapse rate, expressed by the rate ratio, between the higher and approved dose of ocrelizumab arms in patients with RMS and regardless of adherence to the randomized treatment or use of an approved MS DMT medication.

**Summary Measure and Primary Estimator:** The rate ratio will be used to quantify the ratio of the annualized relapse rate, and will be estimated from fitting a negative binomial regression model to the number of relapses. The mean function of the model will be parameterized by using the log link function and the linear predictor will include log time in study (years) as an offset, an indicator variable of the randomized treatment and the randomization stratification factors as independent variables. The statistical significance of the estimated rate ratio will be calculated by using the Wald test.

In order to estimate the estimand of interest, the following **intercurrent event** handling strategies will be applied:

**Early discontinuation from study treatment:** All available data pre and post treatment discontinuation will be included in the analysis following the treatment-policy strategy.

**Initiation of an approved MS DMT medication:** All data pre and post initiation of alternative MS treatment will be included in the analysis following the treatment-policy strategy.

**Pregnancy:** All data pre and post pregnancy onset will be included in the analysis following the treatment-policy strategy.

**Death:** This is anticipated to be very rare, but in case of occurrence, it will be handled with the hypothetical strategy. That is, data on relapse after death will be treated as missing.

Missing data resulting from patients that withdraw their consent to participate in the study and/or a serious CGP breach will not be imputed.

#### **4.5 SAFETY ANALYSES**

The safety analysis set (SAS) is described in Section 3. All safety parameters will be summarized and presented in tables on the basis of this analysis set. Randomized patients who receive incorrect therapy will be summarized in the group according to the rules laid out in Section 3. Patients who received at least one dose of ocrelizumab above 600 mg will be grouped in the higher dose of ocrelizumab arm.

Patients who are not randomized but who receive study drug will be included in the SAS and summarized according to the therapy actually received.

All patients who received at least one infusion (partial or complete) of study drug with patients grouped according to actual treatment received will be included in the analysis.

- The safety data will be summarized regardless of premature study treatment discontinuation or switch to an approved MS DMT medication (including commercial ocrelizumab).
- Additionally, the safety data may also be summarized regardless of premature study treatment discontinuation but until switching to an approved MS DMT medication (including commercial ocrelizumab).

Safety will be assessed through summaries of exposure to study treatment, AEs, changes in laboratory test results, and changes in vital signs. All verbatim AE terms will be mapped to MedDRA thesaurus terms, and AE severity will be graded according to National Cancer Institute Common Terminology Criteria for Adverse Events (NCI CTCAE) v5.0. All AEs, SAEs, AEs leading to death, AEs of special interest, and AEs leading to study treatment discontinuation that occur on or after the first dose of study treatment (i.e., treatment-emergent AEs) will be summarized by mapped term,

appropriate thesaurus level, and severity grade. For events of varying severity, the highest grade will be used in the summaries. Deaths and cause of death will be summarized. Relevant laboratory and vital sign (pulse rate, and blood pressure) data will be displayed by time, with grades identified where appropriate. Additionally, a shift table of selected laboratory tests will be used to summarize the baseline and maximum post baseline severity grade. Changes in vital signs will be summarized.

#### **4.5.1 Extent of Exposure**

Study treatment exposure such as treatment duration, total dose received, and number of doses will be summarized with descriptive statistics.

##### **4.5.1.1 Details in Defining the Number of Doses and Total Dose Received**

The first dose of ocrelizumab is given as two infusions administered 2 weeks apart. If a patient receives any infusion at Dose 1, the patient is counted as having received the first dose.

If a dose is completely missed instead of delayed, the next dose number will be consecutive to the previous dose.

The total cumulative dose is capped at 100%, so the actual dosage for each infusion does not exceed 600 mg or 1200/1800 mg, respectively. The first dose is given in two infusions and the cumulative dose for each of these infusions is also capped at 100%.

##### **4.5.1.2 Treatment Duration and Duration under Observation Definitions**

Treatment duration will be calculated as follows:

(Date of the last recorded treatment observation during the DBT phase\* – Date of first dose of the DBT phase), where\* is the Earliest 1) date of last dose received during the DBT phase + 24 weeks; 2) date of CCOD for the primary analysis reporting; 3) date of treatment discontinuation as described in Section 4.1 for patients who discontinued study treatment; 4) date of subject withdrawal from the study; 5) date of death. The duration under observation for a patient will be calculated as follows:

(The latest recorded date in all eCRF and non eCRF prior to CCOD – Date of first infusion in the first dose) + 1

The duration of observation, within a dose, is defined in a similar manner as follows:

(Day prior to first infusion in the n + 1th dose\* – Date of first infusion in the nth dose) + 1

\*With the exception of the last dose received by the patient where the date of last contact is used as defined above. If the last contact is after the date of the clinical cutoff, the date of last contact will be the CCOD.

## **4.5.2      Adverse Events**

AEs will be defined as all AEs including IRRs and serious MS relapses, but excluding non-serious MS relapses. Therefore, those AEs recorded on the AE and IRR case report form (CRF) pages will be included. Refer to Section 4.5.7 for further guidance on MS relapses considered serious AEs.

For each recorded AE, the term entered by the investigator describing the event (the “reported term”) will be assigned a standardized term (the “Preferred Term” [PT]) and assigned to a superclass term on the basis of the MedDRA World Health Organization (WHO) dictionary of terms. All analyses of AE data will be performed using the PTs unless otherwise specified.

For all summary tables, the AEs will be sorted by SOC (in decreasing order of overall incidence) and then by PT (in decreasing order of overall incidence). All summaries and listings of AEs will be based on the SAS, unless stated otherwise. Summaries of AEs will be generated to summarize the incidence of treatment-emergent AEs only. Treatment-emergent events are defined as those AEs with an observed or imputed date of onset on or after the start date of trial treatment or with CRF flag “Event occurred prior to first study drug administration” equals “no”. If the onset date of the AE is prior to the day of first dose, the AE will be considered treatment-emergent only if the most extreme intensity is greater than the initial intensity (i.e., the intensity for a given AE increases and its end date is on or after the date of the first dose). An AE with a completely missing, non-imputed start date will be assumed to be treatment emergent unless the AE has a complete, non-imputed end date that is prior to the date of the first dose.

AEs will be assigned to a dose if the AE onset date is on or after the date of the first infusion of that dose but before the first infusion of the next treatment dose. AEs that are reported during the SFU period (including the B-cell monitoring period) will be assigned to the last dose received. Hence, the last dose for a patient may be of a variable length, from 24 to 72 weeks or longer. AEs that start prior to the first dose and worsen during treatment (i.e., treatment-emergent) will be assigned to the first treatment dose.

The number of patients who experienced a related AE will be summarized by SOC and PT. AEs will be summarized by SOC and PT by intensity grade. Multiple occurrences of the same event within a patient will be counted once at the greatest intensity/highest grade for this PT. For AEs leading to death, the most extreme intensity will be overwritten by Grade 5 (death). Any AEs and the SOC overall rows of the summary table will count patients according to AEs by intensity (grade).

All patient deaths, regardless of treatment received, will be listed.

SAEs will be defined as all SAEs including serious MS relapses and serious IRRs. The number of patients who experienced an SAE will be summarized by SOC and PT.

Related SAEs will be summarized by SOC and PT. Additionally, the most frequent SAEs ( $\geq 1\%$ ) will be presented by SOC and PT.

A patient may experience an AE that leads to the discontinuation of his/her study treatment. Discontinuation of study treatment for an AE may not necessarily lead to discontinuation from the study because the patient can remain in the DBT phase without treatment. Only AEs that led to the discontinuation of study treatment are of interest. Patients who withdraw early from the study because of AEs will be summarized under disposition. The number of patients who experienced an AE that led to discontinuation of study treatment will be summarized by SOC and PT. The number of patients who experienced an AE that led to modification or interruption of study drug will be summarized by SOC and PT.

For each treatment group, the incidence count for each AE PT will be defined as the number of patients reporting at least one treatment-emergent occurrence of the event. The incidence rate will be calculated as the incidence count divided by the total number of patients in the population. Each table will also present the overall number of patients experiencing at least one AE and the total number of AEs reported (multiple occurrences of the same AE in 1 patient will be counted only once).

The rate per 100 patient-years by treatment group (along with the 95% CI) will be calculated for specific events of interest such as all AEs, SAEs, infections and serious infections (see Section 4.5.4), opportunistic infections (OIs; see Section 4.5.5), and malignancies (see Section 4.5.6).

- The number of AEs per 100 patient-years is calculated as:

$(\text{Total number of AEs} \div \text{Total number of patient-years}) \times 100$

- The 95% CI for the number of AEs per 100 patient-years will be calculated using the exact method based on the Poisson distribution ([Sahai and Khurshid 1993](#)):

Exact lower 95% confidence limit =  $\text{chisq}(p=0.025, df=2Y) / (2T)$

Exact upper 95% confidence limit =  $\text{chisq}[p=0.975, df=2(Y+1)] / (2T)$

where Y is the total number of AEs, T is total number of patient-years at risk and  $\text{chisq}(p, df)$  is the quantile of the upper tail probability of the Chi-squared distribution with df degrees of freedom. This approach has the advantage of providing an estimate for the upper 95% confidence limit even when the total number of AEs is zero.

The rates per 100 patient-years will be summarized by dose and by treatment (including all doses).

To assess the impact of coronavirus disease-2019 (COVID-19) pandemic, AEs may be summarized both including and excluding COVID-19 related AEs.

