The rate per 100 PY of infection was 102 (95% CI: 95.8, 109) in the placebo group, compared with 110 (95% CI: 103, 116) in the ocrelizumab 400 mg group, 118 (95% CI: 111, 126) in the ocrelizumab 1000 mg group, 83 in the ocrelizumab 1500 mg group (95% CI: 49, 132) and 145 (95% CI: 99, 203) in the ocrelizumab 2000 mg group.

The majority of infections were grouped to the SOC Infections and Infestations, with very few events coded to other SOCs and detected by the broader definition. The majority of infections were of bacterial or viral origin.

The most common infections by Preferred Term, reported with a frequency of $\geq 5\%$ in any of the treatment groups, were upper respiratory tract infection, followed by nasopharyngitis, urinary tract infection, bronchitis, and sinusitis. The frequency of all other common AEs were relatively balanced across groups.

The majority of infections in each treatment group were classified by the investigators as Grade 1 or 2 in intensity. Reports of Grade 3 events were higher in the ocrelizumab 400 mg (2.6%; 31 patients) and ocrelizumab 1000 mg (3.2%; 30 patients) groups, compared with placebo (1.7%; 17 patients). One Grade 3 infection was reported with 2000 mg ocrelizumab. There were two Grade 4 events (one patient each in the placebo and ocrelizumab 400 mg group), and six infections resulting in death. Two of the deaths occurred in the ocrelizumab 400 mg group and four in the ocrelizumab 1000 mg group.

Serious Infections

The proportion of patients reporting a serious infection was higher in ocrelizumab 1000 mg group (5.1% of patients; 66 events) compared with the placebo (3.4%; 36 events) and ocrelizumab 400 mg (3.8%; 52 events). No serious infections were reported for patients receiving 1500 mg or 2000 mg ocrelizumab.

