The rate per 100 PY of serious infections was also higher in the ocrelizumab 1000 mg group (7.28; 95% CI: 5.63, 9.27) and ocrelizumab 400 mg group (5.18; 95% CI: 3.87, 6.79) compared with the placebo group (3.99; 95% CI: 2.79, 5.52). The rate of serious infections did not increase with subsequent ocrelizumab doses for any treatment group. The majority of serious infections were captured within the SOC of Infections and Infestations with more reported in the ocrelizumab 1000 mg group (4.9%; 46 patients) compared with the placebo (3.0%; 29 patients) and ocrelizumab 400 mg (3.6%; 43 patients) groups. There was no particular type of infection that contributed to the higher frequency in the ocrelizumab 1000 mg group.

Pneumonia was the most commonly reported serious infection and incidence was generally similar across placebo (1.0%; 10 patients), ocrelizumab 400 mg (0.7%; 8 patients), and ocrelizumab 1000 mg (1.2%; 11 patients) groups. Most of the serious infections with identified pathogen were of bacterial origin.

Overall, data from the RA cohort indicated that ocrelizumab treatment might increase the risk of serious infections for Asian patients/patients in Asia on chronic steroid treatment, notably on the ocrelizumab 1000 mg dose. However, these observations do not reach statistical significance and the Asian region is confounded with Asian race, lower body weight, as well as increased drug exposure.

1.2.3 Statistical Analysis Modelling for the Prediction of SIE rates in MS population from the RA Data

[figure not shown]
Additional exploratory analysis was performed to assess the risk of serious infections in the MS population based on the pooled RA data for 400 mg and 1000 mg doses.

[Figure 11A-1](#) shows that when adjusting the rates of serious infections in RA for various risk factors (geographical region, gender, age, use of steroids and/or methotrexate, levels of IgM and Neutrophils) and predicting the rates of serious infections in MS population with baseline characteristics as observed in the OPERA I and II studies (such as younger average age, no use of steroids or methotrexate, no patients from Asia), no dose dependent increase in serious infections rate in MS up to 1000 mg is expected.

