### **4.5.4            Infections**

Infections will be defined from the AE data using the MedDRA SOC of “Infections and infestations”. Infections will be classified according to the pathogen type (e.g., bacterial, fungal, viral, parasitical, unknown).

An infection will be defined as serious if the event is an SAE as defined in Section 4.5.2.

The number of patients who experienced an infection will be summarized by SOC and PT and by intensity.

The number of infections experienced by more than 5% of patients will be summarized by SOC and PT.

The number of patients who experienced a serious infection will be summarized by SOC and PT.

Identified pathogen codes will not be summarized but will only be listed within the listings of infections and serious infections. Infections and serious infections will be summarized by pathogen types.

The rate per 100 patient-years by treatment group (along with the 95% CI) will be calculated for infections and serious infections overall and by dose/year of exposure based on the number of patient-years observation for the specific dose.

For infections and serious infections, the incidence rate ratio will be calculated. For these analyses, the incidence rate ratio with 95% CI based on the Poisson distribution exact method will be presented.

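### Exact Poisson intervals for AE rates and the infection rate ratio ignore repeat events within patients, and the printed formula reverses the limits and drops the factor of 100

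*SAP*

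**What the plan says.** SAP 4.5.2 (Adverse Events) defines the rate as total AEs divided by total patient-years, times 100. It gives this rate for all AEs, SAEs, infections, serious infections, opportunistic infections and malignancies. On precision it says: "The 95% CI for the number of AEs per 100 patient-years will be calculated using the exact method based on the Poisson distribution". The limits are printed as chisq(p=0.025, df=2Y)/(2T) for the lower and chisq(p=0.975, df=2(Y+1))/(2T) for the upper. Y is the total number of AEs and T the total patient-years. The note below them says that chisq(p, df) "is the quantile of the upper tail probability of the Chi-squared distribution".

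SAP 4.5.4 (Infections) adds a comparison between doses for infections and serious infections: "the incidence rate ratio with 95% CI based on the Poisson distribution exact method will be presented". It does not say whether the numerator is events or patients.

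Two other counting rules stand in 4.5.2. For the summary tables, "the incidence count for each AE PT will be defined as the number of patients reporting at least one treatment-emergent occurrence of the event", and for the table totals, "multiple occurrences of the same AE in 1 patient will be counted only once". The SAP does not say whether either rule applies to Y or to the rate ratio.

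For relapses, another recurrent count, SAP 4.4.6 fits a negative binomial model with log time in study as offset.

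**The concern.** A Poisson interval on a total event count is valid if events occur independently at a common rate. AEs and infections do not behave this way: some patients have several and many have none. The variance of the total then exceeds the Poisson variance, and the interval is too short. Removing repeats of the same term reduces the problem but does not end it, because one patient can still contribute several different terms.

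Infection is listed as an identified risk in Protocol 5.1.1.1.2, and the trial asks whether a doubled or tripled dose adds risk. The rate ratio is the planned comparison of infection rates between doses with an interval. If it is too narrow, it can suggest a dose effect that is not there, or look tighter around 1 than the data allow.

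The formula raises a second, independent problem. With upper-tail quantiles the printed lower limit is the larger number, and neither limit is on the scale of the estimate it accompanies.

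**Working it through.** **1. The formula against a published interval.** Protocol Appendix 11 (Section 1.2.2, Serious Infections) gives 66 events and a rate of 7.28 per 100 patient-years (95% CI 5.63 to 9.27) for RA 1000 mg. So T = 66/0.0728 = 906.6 patient-years.

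- Lower-tail quantiles, times 100: 5.63 to 9.26, which agrees with the published interval to rounding. The 400 mg and placebo intervals also reproduce (3.87–6.79 and 2.79–5.52). The lower tail was evidently intended.
- As printed (upper tail): 'lower' 0.0914 and 'upper' 0.0573, beside an estimate of 7.28. Times 100, these are 9.14 and 5.73. Swapping the labels does not repair them, because the degrees of freedom sit on the wrong tails: 5.73–9.14 is narrower than 5.63–9.26.
- Zero events in 100 patient-years: the correct upper limit is 3.69 per 100; the printed formula gives 0.025 per 100 even after multiplying by 100. The SAP names the zero-event upper limit as an advantage of this method.

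**2. Clustering in the RA data.** With μ events per patient, Poisson expects N(1 − e^(−μ)) patients to have at least one. For a negative binomial with shape k, the share is 1 − (1 + μ/k)^(−k) and the variance inflation is 1 + μ/k. A smaller k means more clustering. Placebo N = 506/0.516 = 981.

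| Serious infections | N | Events | Patients observed | Poisson expects | k | Inflation |
|---|---|---|---|---|---|---|
| Placebo | 981 | 36 | 33 (3.4%) | 35.3 | 0.30 | 1.12 |
| 400 mg | 1186 | 52 | 45 (3.8%) | 50.9 | 0.16 | 1.28 |
| 1000 mg | 947 | 66 | 48 (5.1%) | 63.8 | 0.096 | 1.73 |

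For all infections, patient-years follow from the serious-infection figures: 36/0.0399 = 902, 52/0.0518 = 1004 and 66/0.0728 = 907. With rates of 102, 110 and 118 per 100 patient-years, μ = 0.94, 0.93 and 1.13.

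| All infections | Observed share | Poisson share | k, equal follow-up | k, follow-up uniform on 0 to twice the mean |
|---|---|---|---|---|
| Placebo | 51.6% | 60.9% | 1.47 | 4.34 |
| 400 mg | 50.8% | 60.6% | 1.35 | 3.56 |
| 1000 mg | 55.9% | 67.7% | 1.33 | 3.49 |

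Inflation is 1.64–1.85 with equal follow-up and 1.22–1.32 with very unequal follow-up. The unequal follow-up would explain 61–65% of the gap in shares. It does not remove the excess.

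**3. What this does to the trial's rate ratio.** SAP 2.2 gives 865 patients; at 2:1 this is about 577:288. The minimum treatment period is 120 weeks, about 2.3 years. A mean follow-up of 3.2 years, the event rates and k are assumptions. Counts were simulated as negative binomial with no difference between arms (100,000 runs) and tested with the exact conditional (binomial) method. The table shows how often the interval excludes 1 at 3.2 years.

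| Events per patient-year | No clustering | k = 4 | k = 2 |
|---|---|---|---|
| 0.5 | 4.6% | 9.5% | 13.7% |
| 0.8 | 4.8% | 12.2% | 18.8% |
| 1.1 | 4.7% | 14.9% | 23.0% |

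- At 2.3 years the ranges are 8–12% (k = 4) and 11–19% (k = 2).
- A patient-level robust variance gave 4.6–5.9% (k 2 to 4, 4,000 runs).
- Serious infections at 0.01 and 0.02 per patient-year: 3.3% and 4.0% at k = 2; 6.1% and 10.3% at the RA 1000 mg value of k = 0.096; 3.1% and 3.5% with no clustering.

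**The case against.** - **The intervals are descriptive.** Section 4.5 has no safety hypothesis or decision rule, and patients with an infection are tabulated as well. This stands, and it limits the consequence to interpretation. It does not make a 95% label correct.
- **The size rests on assumptions.** The documents give no dispersion or infection rate for this trial. The RA source pools seven studies, defines infection more broadly than SAP 4.5.4, and covers patients with other risk factors such as steroid and methotrexate use. This stands too, so the results are given as a range. The k = 4 column is close to the weakest clustering found after allowing for very unequal follow-up.
- **The ratio may count patients.** SAP 4.5.2 defines an incidence rate as patients with an event divided by patients, and SAP 4.5.4 speaks of an incidence rate ratio. On that reading there are no repeat events to cluster. But a patients-over-patients proportion does not fit an exact Poisson ratio that directly follows rates per 100 patient-years. The ambiguity is real; the event reading is the more natural one.
- **The once-per-patient rule may apply to Y.** The simulations do not cover that case. Clustering would be weaker by an amount that cannot be estimated from the documents.
- **Serious infections are hardly affected.** This is correct at k of 2 to 4.
- **The formula error is only a wording slip.** The p-values and degrees of freedom are indeed those of the standard limits, and crossed limits would be noticed in output. A near-zero upper limit at zero events is easier to miss, and zero counts are plausible for opportunistic infections and malignancies.

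**Conclusion.** The concern holds, at the level of a change that should be made.

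The formula part is certain: as printed, it gives wrong limits on the wrong scale.

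The clustering part is certain in direction for rates based on total events, and uncertain in size. Under the assumed rates and follow-up, the rate-ratio interval for all infections errs about two to five times as often as its label says (9–15% at k = 4, 14–23% at k = 2, against 5%). This rests on the numerator being events and on RA-like dispersion. The arm-specific rates for all AEs and all infections are too narrow for the same reason. For serious infections at 0.01–0.02 per patient-year the effect is small unless clustering is as strong as in the RA 1000 mg arm. No confirmatory test is affected.

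**What to change.** 1. In SAP 4.5.2, define chisq(p, df) with the lower tail and multiply both limits by 100.
2. State for Y, and for the numerator of the rate ratio in 4.5.4, whether all events count or the once-per-patient rule applies.
3. For all AEs, SAEs, infections and serious infections overall, take rates, rate ratios and 95% CIs from a patient-level robust variance, or from a negative binomial model with a log patient-years offset as in 4.4.6.
4. Keep exact Poisson for first-event or sparse counts (opportunistic infections, malignancies, serious infections by dose) and as the fallback if a model does not converge. At 0.01–0.02 serious infections per patient-year, one 24-week dose period yields only 2.7–5.3 expected events in the higher-dose arm and 1.3–2.6 in the approved-dose arm.

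The cost is SAP wording and a little programming, with no new data. Intervals for common events will be wider.

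### SAP 4.5.2 misstates the exact Poisson limits for adverse-event rates: the chi-square quantile is defined by the wrong tail and the factor of 100 is missing (minor)

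*SAP*

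**What the plan says.** SAP Section 4.5.2 defines the rate first: "The number of AEs per 100 patient-years is calculated as" total events divided by total patient-years, times 100. For the interval it states: "The 95% CI for the number of AEs per 100 patient-years will be calculated using the exact method based on the Poisson distribution". With Y the event count and T the patient-years at risk, the limits are:

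- lower = chisq(p = 0.025, df = 2Y) / (2T)
- upper = chisq(p = 0.975, df = 2(Y + 1)) / (2T)

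The accompanying explanation says that chisq(p, df) "is the quantile of the upper tail probability of the Chi-squared distribution with df degrees of freedom". It adds, as a merit of the method, that an upper limit is available when no events occur.

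Section 4.5.2 plans these intervals for all AEs, SAEs, infections, serious infections, opportunistic infections and malignancies, and has the rates summarised by dose as well as by treatment. Sections 4.5.4 to 4.5.6 repeat the plan for the last four. No other part of the SAP redefines chisq, T or the scale.

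**The concern.** The definition and the probabilities contradict each other. If p is an upper-tail probability, p = 0.025 picks out the large quantile and p = 0.975 the small one, so the limit labelled lower is computed from the large quantile and the limit labelled upper from the small one. The stated p values and degrees of freedom are right only if p is a cumulative (lower-tail) probability.

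The scales also differ. The rate is per 100 patient-years. The limits divide by 2T with T in single patient-years and are never multiplied by 100, so they are per patient-year.

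The SAP says that it supersedes the protocol's analyses for regulatory filing, so an independent programmer should be able to reproduce its intervals from its text. Low counts are where a mistake could pass unnoticed, and they are foreseeable: Protocol Section 5.1.1.1.2 reports no opportunistic infections in ocrelizumab-treated MS patients during the controlled period of the pivotal trials.

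**Working it through.** **Inputs.** The SAP gives a formula but no worked number. Protocol Appendix 11, Section 1.2.2 (Serious Infections) gives counts, rates and 95% intervals of the same kind from the pooled rheumatoid arthritis data. For example: "The rate per 100 PY of serious infections was also higher in the ocrelizumab 1000 mg group (7.28; 95% CI: 5.63, 9.27"). The counts there are 66 (1000 mg), 52 (400 mg) and 36 (placebo). Patient-years are not stated, so they are back-calculated as T = 100 × Y / rate:

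- 1000 mg: 100 × 66 / 7.28 = 906.6
- 400 mg: 100 × 52 / 5.18 = 1003.9
- placebo: 100 × 36 / 3.99 = 902.3

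**Step 1: which reading reproduces the protocol?** Each cell shows the limit labelled lower, then the limit labelled upper.

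| Group | Protocol interval | Lower-tail quantile, ×100 | Upper-tail quantile, ×100 | SAP taken literally (upper tail, no ×100) |
|---|---|---|---|---|
| 1000 mg, Y = 66 | 5.63, 9.27 | 5.63, 9.26 | 9.14, 5.73 | 0.0914, 0.0573 |
| 400 mg, Y = 52 | 3.87, 6.79 | 3.87, 6.79 | 6.68, 3.95 | 0.0668, 0.0395 |
| placebo, Y = 36 | 2.79, 5.52 | 2.79, 5.52 | 5.395, 2.89 | 0.0539, 0.0289 |

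Only the lower-tail quantile with the factor of 100 works. The gap between 9.26 and 9.27 is rounding: a true rate of 7.285 would scale 9.2619 to 9.2619 × 7.285 / 7.28 = 9.268.

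**Step 2: does the reversal hold generally?** Both limits divide by 2T, so their order does not depend on T. Using an assumed T = 1000 patient-years, the upper-tail definition and the factor of 100:

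- Y = 1: lower 0.369, upper 0.024 (correct: 0.0025 to 0.557)
- Y = 10: lower 1.709, upper 0.549 (correct: 0.480 to 1.839)
- Y = 100: lower 12.05, upper 8.23 (correct: 8.14 to 12.16)

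The order was reversed at every count checked from 1 to 500.

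**Step 3: zero events.** The lower limit is 0, so nothing reverses. The upper limit uses 2 degrees of freedom, where the quantile with cumulative probability c is −2 ln(1 − c). With T = 1000 and the factor of 100 in both cases:

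- lower-tail 0.975: −2 ln(0.025) / 2000 × 100 = 0.369 per 100 patient-years
- upper-tail 0.975 (cumulative 0.025): −2 ln(0.975) / 2000 × 100 = 0.0025 per 100 patient-years

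The ratio is ln(0.025) / ln(0.975) = 3.689 / 0.02532, about 146, whatever T is. This is the tail error alone. The literal formula, without the factor of 100, gives 0.000025 per patient-year.

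**The case against.** The strongest reply is that the intended method is unmistakable. The SAP names the exact Poisson method, cites a source, labels the limits, pairs 0.025 with 2Y and 0.975 with 2(Y + 1), and says the interval is for a rate per 100 patient-years. One explanatory phrase conflicts with all of that, and one multiplication is left out. Standard software would probably return the right limits, and the protocol's earlier intervals follow the correct formula. For one or more events, a literal implementation would print a lower limit above the upper one, and ordinary output checks should catch that. This stands, and it is why the point is minor. It does not fully cover zero events: there the output is in the right order, and an upper limit close to 0 might be taken at face value.

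Two stronger readings are tempting, and the documents do not support them.

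- A reader might infer that the trial's main comparative safety result is at risk. These are single-arm descriptive intervals. The between-arm measure, an incidence rate ratio with its own exact Poisson interval, is specified separately in SAP Section 4.5.4 for infections and serious infections, and this formula is not part of it.
- A reader might infer that the reported intervals will be too narrow. That would need a second mistake: a programmer exchanging the two labels while leaving the degrees of freedom where they are. At 66 events this gives 5.73 to 9.14 instead of 5.63 to 9.26. Coverage would be about 93.5% at 66 expected events and 55% at 1. Nothing in the SAP asks for such a swap.

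**Conclusion.** The text is wrong as written in two respects, the tail convention and the scale, and nothing elsewhere in the SAP corrects it. Followed literally, it gives reversed limits on the wrong scale for any count of one or more. At zero events it gives an upper limit about 146 times too low from the tail error alone, which defeats the advantage that the SAP claims for the method. The method itself is sound.

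The effect is confined to descriptive per-arm rates. Alpha, power and the primary analysis are untouched. Severity is minor: this is a specification error, not evidence that reported numbers will be wrong.

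The conclusion does not depend on the assumed exposures. Patient-years for the three protocol examples are back-calculated from rounded rates, and 1000 patient-years is purely illustrative. The reversal and the 146-fold ratio hold for any T.

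**What to change.** In SAP Section 4.5.2:

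1. Define chisq(p, df) as the quantile with cumulative (lower-tail) probability p. Keeping the upper-tail definition and exchanging the two p values is equivalent. Exchanging only the labels of the limits is not, because 2Y and 2(Y + 1) would then sit on the wrong limits.
2. Multiply both limits by 100, or define T in units of 100 patient-years for the limits.
3. State that the lower limit is 0 when Y = 0. This is the usual convention, and the SAP does not spell it out.

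The cost is about one sentence of SAP wording. No data collection, sample size or other analysis changes. Rerunning the three protocol examples above would confirm that the programmed version is right.
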